### 9.4. Rules of display of the value

Case	Rules of display
When the value cannot be calculated	Hyphen, “-”

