The last date of the final treatment with this drug	
Of dates described in “Administration status of this drug” in survey sheet, records corresponding to following conditions should not be used for analysis.
 
Records of patients who started to receive this drug by August 15, 2013: The start date of the initial treatment with this drug + 1092 days < the start date
 
Records of patients who started to receive this drug between August 16, 2013 and August 15, 2014: The start date of the initial treatment with this drug + 728 days < the start date
 
Records of patients who started to receive this drug between August 16, 2014 and August 15, 2015: The start date of the initial treatment with this drug + 364 days < the start date
 
Of the last date of the treatment complemented by following [1] to [4], the latest date should be the last date of the final treatment with this drug.
 
[1] Data should be sorted by the start date of the treatment, separate volume, and the number of the cycle of treatment described in “Administration status of this drug” in that order.
 
[2] The start date of each data should be complemented at the last date of the initial and second treatment with this drug.
 
When a date is described in the section for the last date of the third or subsequent treatment, and there is no check mark in “Ongoing” box so that last date of the treatment can be

Name of data	Derivation and calculation method

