	
identified, the date described as the last date of the treatment should be employed.
 
[3] When there is no description in the section for the last date of the third or subsequent treatment or there is a check mark in “Ongoing” box so that the last date of the treatment cannot be identified, following rules are applied.
 
 
● When the patients are included in the last period in the volume: The date should be complemented by the last follow-up date for relevant volume or a date obtained by subtracting 1 day from start date of the subsequent treatment, which is earlier.
 
● When the patients are included in not last period in the volume: The date should be complemented by a date obtained by subtracting 1 day from the start date of the subsequent treatment with this drug.
 
 
The last follow-up date should be defined as follows:
 
 
• The initial volume: Start date of the treatment with this drug + 364 days
 
• The second volume: Start date of the treatment with this drug + 728 days
 
• The second volume: Start date of the treatment with this drug + 1092 days
 
 
[4] When there is description in the section for the last date of the third or subsequent treatment but the date is incomplete so that the last date of the treatment cannot be identified, following rules are applied.
 
 
● When the date include year and month, but date is unknown: The date should be complemented by the last date of relevant month.
 
● When the date include year, but month and date is unknown: The date should be complemented by the last date in the last month of relevant year. In addition, when records in the subsequent treatment are created and the start date of the subsequent treatment is earlier than the complemented last date in the last month of the relevant year, the last date of the treatment should be complemented by the date obtained by subtracting 1 day from the start date of the subsequent treatment.
 
 
However, if description in the last date of the treatment in the records for which last date of the treatment was complemented according to above rules and there is a check mark in “Ongoing” box, following rules are applied:
 
 
● When the described last date of the treatment is later than the last date complemented according to above rules, the date complemented should be employed as the last date of the final treatment of this drug.
 
● When the described last date of the treatment is earlier than the last date complemented according to above rules, the date described should be employed as the last
 

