Patients in whom dose increase was made	
Patients in whom 160 mg/2 weeks was administered as the initial dose, 80 mg/2 weeks as the second dose, 40 mg/2 weeks as the third and subsequent dose, and 160 mg or 80 mg was administered at least once thereafter are applicable.

Administration status (total number of administrations, dose)	
 
The number of administrations 
 
[1] Data should be sorted by the start date of the treatment, separate volume, and the number of the cycle of treatment described in “Administration status of this drug” in that order.
 
[2] Administration intervals should be calculated by administration status.
 
 
 
The administration interval should be 14 days for the initial and second administration.
 
The third and subsequent administration should be given according to following rules.
 
If there is a check mark in “once/2 weeks” box, the administration intervals should be 14 days, and in any other situations, a data should be obtained from “[HUMIRA BD] converted data to be provided for analysis”.
 
[3] The number of administrations by administration status should be calculated.
 
The number of administrations = (The last date of the administration (after complement) - the start date of the administration (after complement))/the administration intervals (days)
 
[4] Result obtained according to [3] is larger than 0 and smaller than 1, the number of administrations should be 1.
 
In addition, that number is 1 or larger, the number of administrations should be obtained by rounding off the decimal point.
 
[5] The number of administrations should be sum total of [4] by patients
 
 
Dose 
 
[1] If the dose of this drug is classified as other, the data should be obtained from “[HUMIRA BD] converted data to be provided for analysis”.
 
[2] The dose by administration status should be calculated.
 
 
 
The dose = The number of administrations × the dose
 
[3] Total dose should be sum total of [2] by patients
 
 
Mean daily dose 
 
Mean dose = Total dose/Total number of administrations
 
 
 
 

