## 11. Method of dividing hierarchy of data

data	Method of dividing hierarchy
Dosage and administration	160mg→80mg→40mg/2 weeks, no changes thereafter 160mg→80mg→40mg/2 weeks, and 160mg or 80mg is administered at least once thereafter 160mg, and not administered thereafter 160mg→80mg, and not administered thereafter 80mg, and not administered thereafter 40mg, and not administered thereafter others
the number of administrations	at least once and less than 4 times at least 4 times and less than 12 times at least 12 times and less than 26 times at least 26 times and less than 39 times at least 39 times and less than 52 times at least 52 times and less than 65 times at least 65 times and less than 78 times at least 78 times
Total dose	lower than 500mg at least 500mg and lower than 1000mg at least 1000mg and lower than 2000mg, at least 2000mg and lower than 3000mg at least 3000mg unknown
Mean daily dose	lower than 40 mg at least 40 mg and lower than 60 mg at least 60 mg and lower than 80 mg at least 80 mg and lower than 100 mg at least 100 mg unknown

data	Method of dividing hierarchy
Administration duration	at least 0 week and shorter than 4 weeks (1-28 days) at least 4 week and shorter than 12 weeks (29-84 days) at least 12 weeks and shorter than 24 weeks (85-168 days) at least 24 weeks and shorter than 52 weeks (169-364 days) at least 52 weeks and shorter than 104 weeks (365-728 days) at least 104 week and shorter than 156 weeks (729-1093 days) unknown * When the start date of the administration is defined as 1
Reasons for discontinuation	Occurrence of adverse events, insufficient effect, patient's request, not visiting, others, multiple reasons, unknown, and not described
Sex	male, female, unknown, not described
Pregnancy/lactation	Without pregnancy/lactation, during pregnancy, during lactation, unknown, not described
Race	Japanese, other Asians, others, unknown, not described
Age (years)	Younger than 15 years, 15 years or older and younger than 65 years, 65 years or older, unknown/not described
Body weight (kg)	Lower than 30, 30 or higher and lower than 40, 40 or higher and lower than 50m, 50 or higher and lower than 60, 60 or higher, unknown/not described
Body height (cm)	Lower than 140, 140 or higher and lower than 150, 150 or higher and lower than 160, 160 or higher and lower than 170, 170 or higher and lower than 180, 180 or higher and lower than 190, 190 or higher, unknown/not described

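### The administration count in SAP 10.1 has no rule for a result of exactly 0, so as written the first two doses (240 mg on the tabulated sequence) are not counted

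*SAP*

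**What the plan says.** Two entries in SAP 10.1 work together here.

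The entry on the last date of the final treatment fills in end dates. For the first two treatments rule [2] states: "The start date of each data should be complemented at the last date of the initial and second treatment with this drug". The alternative of using the day before the next start is in rule [3], which opens with "When there is no description in the section for the last date of the third or subsequent treatment" and so does not reach the first two doses.

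The entry on total number of administrations and total dose then counts. Step [2]: "The administration interval should be 14 days for the initial and second administration". Step [3] takes "The last date of the administration (after complement) - the start date of the administration (after complement" and divides by the interval in days, with no 1 added. Step [4] has two branches. The lower one is: "Result obtained according to [3] is larger than 0 and smaller than 1, the number of administrations should be 1". The upper one rounds any result of 1 or more. Step [5] sums the counts within a patient. Dose per record is count times dose, and the mean dose is total dose over total count.

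Section 11 bands these values. The lowest count band is "at least once and less than 4 times" and the lowest total-dose band is "lower than 500mg".

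**The concern.** The two branches of step [4] leave out exactly one non-negative value, 0, and the end-date rule puts the first and second dose on that value in every patient to whom it is applied. It is the normal case, not a rare one. A later record that starts and ends on the same day falls into the same gap.

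A programmer who follows the text gets either 0 or a missing value for these records, and neither is right. Table 1.6 (exposure in the safety and efficacy populations) and Table 2.3 items (14) and (17) would be wrong. So would mean daily dose, one of the 28 factors tested in Tables 2.9 and 3.4. The patients hit hardest are those who stop after one or two doses. Their count of 0 has no band in section 11, and their mean is 0/0, which section 9.4 shows as a hyphen ("When the value cannot be calculated"). If that mean is then classed as unknown, section 9.5 removes them from the mean-dose tests.

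**Working it through.** The SAP prints no total for this derivation, so there is no stated figure to reproduce. The check applies the rules as written, then repeats them with a result of 0 counted as 1.

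**Inputs.** First dose 160 mg, second 80 mg, then 40 mg every 2 weeks (10.1, dosage and administration). Last follow-up dates are start + 364, + 728 and + 1092 days (10.1). Discontinuation cut-offs are + 350, + 700 and + 1064 days (10.1). Assumption for the example: doses 1 and 2 on days +0 and +14, then one 40 mg record from +28 to last date L.

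**Per record.**
- Dose 1: (0 − 0)/14 = 0. Dose 2: (14 − 14)/14 = 0. Neither branch of step [4] applies.
- Later record: k = round((L − 28)/14).
- As written: count k, dose 40k. With 0 counted as 1: count k + 2, dose 40k + 240.

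**Treated to the last follow-up date.**

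| L (days) | k | Count, as written / corrected | Total mg, as written / corrected | Dose difference | Mean mg, as written / corrected |
|---|---|---|---|---|---|
| 364 | 336/14 = 24 | 24 / 26 | 960 / 1200 | −240/1200 = −20% | 40.0 / 46.2 |
| 728 | 700/14 = 50 | 50 / 52 | 2000 / 2240 | −240/2240 = −11% | 40.0 / 43.1 |
| 1092 | 1064/14 = 76 | 76 / 78 | 3040 / 3280 | −240/3280 = −7% | 40.0 / 42.1 |

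**Early stoppers.**
- One dose: 0 against 1 administration, 0 against 160 mg, mean 0/0 against 160 mg.
- Two doses: 0 against 2 administrations, 0 against 240 mg, mean 0/0 against 240/2 = 120 mg.
- Both true means belong in the top mean-dose band (at least 100 mg). The total of 0 mg still falls in the lowest dose band, as 160 or 240 mg would.

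**Band changes in section 11, from each cohort's discontinuation cut-off to its last follow-up date.**
- Count drops one band where k + 2 reaches 26, 52 or 78 and k does not: L = 357–364, 721–728 and 1085–1092.
- Total dose drops one band at L = 350–364 (the whole 52-week window; 920 against 1160 mg at 350), 700–720 and 1064–1070.
- These ranges take rounding off to mean nearest integer. With truncation, the count band changes only at 364, 728 and 1092, and the dose band at 350–364, 700–727 and 1064–1077.

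**Mean-dose band.**
- Constant 40 mg: (240 + 40k)/(2 + k) ≥ 60 requires k ≤ 6, so the band changes only up to 8 injections. With 6 injections, k = 4: 160/4 = 40.0 against 400/6 = 66.7 mg.
- Dose increase (illustrative): 160, 80, 16 × 40, 14 × 80 mg gives 1760/30 = 58.7 against 2000/32 = 62.5 mg, a band change at 32 injections.

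**Counter-check.** If the day before the next start were used for doses 1 and 2, the result would be 13/14 = 0.93, which step [4] lifts to 1, and nothing would be lost. The SAP limits that rule to the third and later treatments.

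**The case against.** The strongest reply is that the SAP is silent on 0 rather than assigning it, and that the intention is plain. Section 11 starts at one administration, and the corrected counts of 26, 52 and 78 land on its cut-points. A programmer would probably count 1, and a patient with no count band would show up in Table 1.6. That is a fair account of the intention, but a derivation rule should not depend on a guess, and the text as it stands excludes 0.

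The link to the end-date rules can also be questioned. Step [3] speaks of completed start dates as well, for which no rule is shown, and the end-date rule sits under a different variable in awkward wording. This makes the link an assumption, but no other rule shown completes the end dates of doses 1 and 2.

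Three limits stand:
- The exact day ranges assume a single later record. Patients followed for 104 or 156 weeks may have several, each rounded separately. The shortfall of 2 administrations and 240 mg does not depend on this.
- If the last date of a later record means the last injection, step [3] would also need a 1 added there. That is a separate question resting on its own assumption. The corrected totals above should therefore not be read as proven injection counts.
- A negative result, possible when two later records share a start date, also remains without a rule.

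**Conclusion.** The concern holds. Applied as written, 10.1 gives no administration and no dose for the first and second treatment, a shortfall of 2 administrations and 240 mg for every patient with both doses on the tabulated sequence. At 52, 104 and 156 weeks this is 20%, 11% and 7% of total dose. One- and two-dose patients are left with no count band and no mean dose.

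The conclusion rests on reading *after complement* in step [3] as the end-date rules of the same section, and on an unassigned result being summed as 0; if it is treated as missing, the totals are short by the same amount or themselves missing.

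The effect is confined to exposure summaries and listings and to one factor in Tables 2.9 and 3.4. Adverse-reaction incidence, overall improvement, days to last administration (which has its own formula with 1 added) and the maximum dose in Table 2.3 item (13) are unaffected. For patients on constant 40 mg treated to the last follow-up date, the mean-dose band does not change. The point should be fixed, but it does not threaten the main safety or efficacy results.

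**What to change.** In 10.1, number of administrations, step [4], change the lower condition to *0 or larger and smaller than 1*, with the count set to 1. This counts the first dose, the second dose and any later same-day record once, and leaves every positive result as it is. It concerns only the counting of recorded doses.

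Two wording corrections can go in at the same time, though the finding does not rest on them. Table 2.3 item (14) prints count before dose for the mean dose, where 10.1 has dose over count; the slash may only separate the two inputs, but the order should match 10.1. The quantity called mean daily dose is a mean per administration and should be labelled so.

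Cost: one line in step [4], one line in Table 2.3 item (14) and one label, then a re-run of Tables 1.6, 2.3, 2.9 and 3.4. No new data are needed.

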## efficacy analysis

Objective of analysis: Distribution of the number of administration, total dose, mean daily dose, days to last date of administration are shown

Analysis items: For the number of administration, total dose, and mean daily dose, the number of patients according to the classifications defined in “11 method of dividing hierarchy of data” and rate of the patients to those included in analysis should be calculated. In addition, summary statistics should be calculated for each measurement. Day to the last date of administration should be calculated according to “days to last date of the final administration of this drug” in “10.1 Overall”, and the number of patients by Time Allowance containing corresponding to days of administration in each patient defined in “12.1 time of evaluation of administration status of this drug” and rate of the patients to those included in analysis should be calculated. Summary of statistics of days of administration should be calculated.

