**“2.19.1 Treatment for patients who showed insufficient response to treatment”**

Patients included in analysis: In patients included in safety analysis, patients who discontinued the survey because of “insufficient effect” or patients in whom dose or the number of administration was adjusted because of “insufficient effect” should be

included.

Objective of analysis: Presence or absence of drugs used after discontinuation of this drug and distribution of the drugs used after discontinuation of this drug are shown.

Analysis items: The number of patients included in analysis should be calculated.

The number of patients and rate of these patients by “drugs used after discontinuation of this drug” and ”detailed classifications of drug used after the discontinuation of this drug“ defined in “11 method of dividing hierarchy for data” should be calculated.

Date of patients in whom dose or the number of administration was adjusted because of “insufficient effect” should be obtained from “[HUMIRA BD] converted data for provision for analysis”.

Notes: Detailed classifications of drug used after the discontinuation of this drug may be overlapped.

“2.19.2 Dosage and administration for patients who showed insufficient response to treatment”

Patients included in analysis: In patients included in safety analysis, patients who discontinued the survey because of “insufficient effect” or patients in whom dose or the number of administration was adjusted because of “insufficient effect” should be included.

Objective of analysis: Distribution of dosage and administration for patients who showed insufficient response to treatment is shown.

Analysis items: The number of patients included in analysis should be calculated.

The number of patients and rate of these patients to those included in analysis should be calculated by presence or absence of discontinuation and classification of dosage and administration (patients discontinued by the initial or second administration, patients who received this drug 3 times or more, the maximum dose for the third or subsequent administration is 40 mg/2 weeks, 40 mg/1 week, 80 mg/2 weeks, 80 mg/1 week, 160 mg/2 weeks, 160 mg/1 week, and others). Items with the number of 0, output by items should not be made.

Date of patients in whom dose or the number of administration was adjusted because of “insufficient effect” should be obtained from “[HUMIRA BD] converted data for provision for analysis”.

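### The variable called mean daily dose is a mean dose per injection; it ignores the injection interval, so Tables 2.9 and 3.4 have no dose factor sensitive to interval

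*SAP*

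**What the plan says.** SAP section 10.1, in the row on number of administrations and dose, builds the variable in steps.

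- **Interval.** "The administration interval should be 14 days for the initial and second administration". From the third administration on, "If there is a check mark in “once/2 weeks” box, the administration intervals should be 14 days"; otherwise the interval comes from a converted data file.
- **Count.** Administrations per record are the record's last date minus its start date, divided by the interval. "Result obtained according to [3] is larger than 0 and smaller than 1, the number of administrations should be 1"; values of 1 or more are rounded.
- **Total dose.** "The dose = The number of administrations × the dose", summed over the patient's records.
- **Mean daily dose.** "Mean dose = Total dose/Total number of administrations".

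Section 11 bands the result under the daily name, starting with "Mean daily dose lower than 40 mg" and ending at 100 mg or more. Table 1.6 reports it: "For the number of administration, total dose, and mean daily dose, the number of patients according to the classifications defined". Tables 2.9 (adverse reactions) and 3.4 (overall improvement) list mean daily dose among the factors to be tested.

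Table 2.19.2 allows for weekly use: "the maximum dose for the third or subsequent administration is 40 mg/2 weeks, 40 mg/1 week, 80 mg/2 weeks, 80 mg/1 week". Table 2.3 item (14) draws on the same 10.1 row but calls the quantity a mean one-time dose, and prints the ratio inverted, with administrations over dose.

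**The concern.** A quantity called daily has no time in it. Shortening the interval adds injections to the denominator and the matching milligrams to the numerator, so the value barely moves. Raising the dose at a fixed interval moves it a great deal. Two patients who receive the same amount of drug over the same time can therefore land in different bands, while two patients whose exposure differs nearly twofold can share one.

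This bears on two uses. The results feed the safety periodic report and the reassessment application, where a daily dose of 40 mg or more would be read as exactly that. And the survey's third objective is to find factors that may contribute to safety and efficacy. Mean daily dose is the only factor in Tables 2.9 and 3.4 that measures amount of drug; total dose and number of administrations are not on either list.

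**Working it through.** The plan states no numerical result for this variable, so there is nothing to reproduce. I applied its algorithm to three illustrative patients.

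**Inputs from the SAP.** Doses of 160 mg, 80 mg, then 40 mg (10.1, dosage row). Weekly and 80 mg use from the third administration on (Table 2.19.2). A 52-week last follow-up date of start + 364 days, and days on drug as last date minus start date plus 1, here 365 (10.1).

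**Assumptions.** The first two doses are given at start and start + 14 days. One unchanged regimen then runs from start + 28 to start + 364 days.

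**Injections from the third record on.** (364 − 28)/14 = 24 two-weekly; (364 − 28)/7 = 48 weekly.

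**Two readings of the first two doses.** Reading A counts each once, adding 2 injections and 160 + 80 = 240 mg. Reading B is literal: the 10.1 row on the last treatment date, step [2], sets the end of each of these two administrations to its own start date. The count is then 0/14 = 0, and the rule that lifts a count to 1 applies only above zero, so both doses drop out.

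| Regimen from third dose | Reading A | Reading B | Band, both readings | True daily mean |
|---|---|---|---|---|
| 40 mg/2 weeks | (240 + 960)/26 = 1200/26 = 46.2 | 960/24 = 40.0 | 40 to <60 | 1200/365 = 3.29 |
| 40 mg/week | (240 + 1920)/50 = 2160/50 = 43.2 | 1920/48 = 40.0 | 40 to <60 | 2160/365 = 5.92 |
| 80 mg/2 weeks | (240 + 1920)/26 = 2160/26 = 83.1 | 1920/24 = 80.0 | 80 to <100 | 2160/365 = 5.92 |

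**Size against a daily mean.** Reading A: 46.15/3.29 = 14.0 two-weekly and 43.2/5.92 = 7.3 weekly. Reading B, against the drug actually given: 40.0/3.29 = 12.2 and 40.0/5.92 = 6.8.

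**Interval.** The weekly patient receives 2160/1200 = 1.8 times the drug of the two-weekly 40 mg patient and stays in the same band. The 80 mg two-weekly patient receives the same 2160 mg over the same 365 days as the weekly patient and sits two bands higher.

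**Other durations, reading A, 40 mg two-weekly against weekly.**

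- 104 weeks: 2240/52 = 43.1 against 4240/102 = 41.6.
- 156 weeks: 3280/78 = 42.1 against 6320/154 = 41.0.
- About 12 weeks (last date start + 83, counts rounded to nearest): 400/6 = 66.7 against 560/10 = 56.0. Here the bands differ, with the weekly patient in the lower one. Reading B gives 40.0 for both.

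**The case against.** The strongest reply is that a per-injection mean was intended and only the label is wrong. The formula line says mean dose, the bands fit nothing but a per-injection value, and Table 2.3 item (14) asks for a mean one-time dose. That stands: a programmer would compute a sensible per-injection mean, and no daily figure is miscalculated. It does not rescue the daily name, nor does it supply an interval-sensitive factor.

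Three stronger readings are tempting and are not supported.

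- A reader might infer that a weekly patient always scores below a two-weekly one. That needs the first two doses counted once each and equal follow-up; on the literal rule they tie at 40.0.
- A reader might take 14-fold as general. It applies to two-weekly dosing; weekly dosing gives about 7.
- A reader might conclude that the survey cannot relate dose intensity to outcome at all. Table 1.6 gives total dose, number of administrations and days. Table 2.19.2 separates weekly from two-weekly use among insufficient responders. The deviation flag is carried in patient list 1.4 beside adverse events and overall improvement.

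What remains is that none of these is a factor in Tables 2.9 or 3.4. The other dose classifications do not help there: weekly 40 mg falls into the residual dosage class, and the dose-increase flag requires a later 80 mg or 160 mg dose.

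It is also fair that Table 2.19.2 provides for weekly categories but suppresses empty ones. The plan allows for weekly use without showing that any occurred.

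**Conclusion.** The point holds in this form. The variable is a mean dose per administration under a daily name, and it does not respond to the injection interval. Under the illustrative histories it is about 14 times a true daily mean for two-weekly use and about 7 times for weekly use over 52 to 156 weeks. At 52 weeks, on either counting reading, 40 mg weekly shares a band with 40 mg two-weekly and is separated from 80 mg two-weekly, whose total and duration it matches. Tables 2.9 and 3.4 therefore contain no dose factor sensitive to interval.

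The dosing histories are assumptions built from the plan's own dose patterns. The number of patients on intervals other than 14 days is not given, so the effect on the survey's results is unknown. It should be corrected before the tables are run. No view is taken on which regimen is right.

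**What to change.** 1. Rename the variable mean dose per administration in sections 10.1 and 11 and in Tables 1.6, 2.9 and 3.4. Reconcile Table 2.3 item (14) with it, in name and in the direction of the ratio (as printed, the first patient above would be listed as 26/1200 = 0.02).
2. State how many administrations the first and second doses contribute, so that 40.0 and 46.2 cannot both be produced from the same record.
3. Add one per-time exposure variable in mg per 14 days: 14 × dose / interval for each record, weighted by the record's days. Taken from the third record on, the three patients above score 14 × 40/14 = 40, 14 × 40/7 = 80 and 14 × 80/14 = 80. Report it in Table 1.6 and use it as the dose factor in Tables 2.9 and 3.4. Say how patients with no third record are classed.
4. Fix its bands before the run.

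The cost is SAP wording, one derived variable from intervals and dates already in the data, and a few table rows. There are two downsides. Bands have to be chosen. And any link with response in Table 3.4 can only be descriptive: Tables 2.19.1 and 2.19.2 provide for dose or frequency being adjusted because of insufficient effect, so exposure may partly follow response.
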